## Analysis Phase

Analysis phase	Start date	End date
Screening	The date of signing the informed consent	1 day before the first study intervention intake
Investigation	Date of the first study intervention intake	If the participants are from Group A, Min [Week 48, study discontinuation]
		If the participants from Group B will not convert to the optional cohort, Min [Week 60, study discontinuation]
		If the participants will convert to the optional cohort, 1 day before the optional investigation phase
Optional investigation	Date of the first BDQ+CAM+EB intake for nonconverters came from Group B	For nonconverters came from Group B, Min [Optional Week 48, study discontinuation]
Follow-up	If the participants are in Group A and moved to follow-up period, end of the investigation phase + 1 day	Min [Week 60, study discontinuation]

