### 5.6.2. Adverse Events

The verbatim terms used in the CRF by investigators to identify adverse events will be coded using the Medical Dictionary for Regulatory Activities (MedDRA version 27.1). Any AE occurring at or after the initial administration of study intervention through the end date of investigation phase defined in Section 5.1 is considered to be treatment emergent. If the event occurs on the day of the initial administration of study intervention, and either event time or time of administration are missing, then the event will be assumed to be treatment emergent. If the event date is recorded as partial or completely missing, then the event will be considered to be treatment emergent unless it is known to be prior to the first administration of study intervention based on partial onset date or resolution date. All reported treatment-emergent adverse events (TEAE) will be included in the analysis of investigation phase and optional investigation phase. All reported adverse events will be included in the analysis of follow-up phase. For each adverse event, the number and percentage of participants who experience at least 1 occurrence of the given event will be summarized by intervention group and analysis phase.

Summary tables will be provided for treatment-emergent adverse events, all adverse events will be presented in a descending order by incidence based on all participants (Total column):

- AEs
- Serious AEs (SAEs)
- AEs leading to discontinuation of study intervention
- AEs by severity
- AEs by relationship to study intervention
- AEs leading to dose interruption/dose modification of the study intervention
- AEs by onset time (at 3-months interval)

In addition to the summary tables, listings will be provided for participants who:

- Had SAEs
- Had AEs leading to discontinuation of study intervention/termination of study participation

Incidence of other treatment-emergent adverse events of special interest will be summarized by intervention group and analysis phase. See [Appendix 8](#) for list of adverse events in each category.

Deaths will be displayed by actual intervention received. Frequencies for the following parameters will be included in the summary table:

- Number of participants who died
- Cause of death
- Relationship to study intervention (yes/no)

A listing of participants who died will be provided.

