### 5.6.3.3. Electrocardiogram

The ECG parameters that will be analyzed are heart rate, PR interval, RR interval, QRS interval, QT interval, and corrected QT (QTc) interval using the correction method, Bazett's formula (QTcB), Fridericia's formula (QTcF).

Bazett's formula:  $QTcB \text{ (msec)} = QT \text{ (msec)} / (RR \text{ (msec)}/1000)^{1/2}$ ; if RR is missing, use  $QT \text{ (msec)} * (HR(bpm)/60)^{1/2}$

Fridericia's formula:  $QTcF \text{ (msec)} = QT \text{ (msec)} / (RR \text{ (msec)}/1000)^{1/3}$ ; if RR is missing, use  $QT \text{ (msec)} * (HR(bpm)/60)^{1/3}$ .

For the time points on which triplicate ECGs apply, a rounded mean value to the nearest integer per triplet will be calculated per time point before any further handling. This round mean value will be used through the entire analysis also in case of 1 or 2 missing values.

ECG records with partial dates (any of day/month/year is missing) will not be used in analysis except in the listings.

If heart rate (HR) is missing, it will be calculated using RR (if available) and rounded to the integer value (see the formula below) before any further handling if applicable.

$$\frac{1000}{RR(ms)} = \frac{HR(bmp)}{60}$$

HR from the vital signs section (ie, pulse) will not be used in this ECG analysis section. RR values (if applicable) will only be listed. Recalculated HR values will be flagged.

The number and percentage of participants with QTc interval will be summarized at each scheduled time point. The number and percentage of participants with QTc interval increases from baseline to the maximum postbaseline value will be summarized. Refer to the following table for summary categories.

Criteria for Abnormal QTc Values and Changes from Baseline	
QTcF/QTcB value	<=450
	>450 – 480
	>480 – 500
	>500
QTcF/ QTcB change from baseline	<=30
	>30 – <=60
	> 60

A shift table will be provided summarizing the shift from baseline to maximum QTc interval classification over time

Descriptive statistics of ECG parameters and change/percent change from baseline will be summarized at each scheduled time point.

If ECG measurements are repeated at a visit, they will be averaged. The averaged value will be considered the 'Visit' ECG result.

Abnormality criteria (based on criteria defined below) will be applied to baseline and postbaseline values.

Postbaseline abnormalities will be compared with their corresponding baseline result:

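### Cumulative investigation-phase safety tables compare arms over unequal planned time (48 weeks in Group A; about 26 to 34 or 60 in Group B), with no common cut-off or person-time

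*SAP*

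**What the plan says.** SAP 5.6.2 counts an adverse event from first dose "through the end date of investigation phase defined in Section 5.1 is considered to be treatment emergent". It then tabulates the number and percentage of "participants who experience at least 1 occurrence of the given event will be summarized by intervention group and analysis phase". The same structure serves SAEs, severity, relatedness, events leading to discontinuation, and AEs of special interest.

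The Analysis Phase table in SAP 5.1 gives the investigation phase three different ends:

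- Group A: "If the participants are from Group A, Min [Week 48, study discontinuation"]. Weeks 48 to 60 fall in a separate follow-up phase.
- Group B, not switching: "If the participants from Group B will not convert to the optional cohort, Min [Week 60, study discontinuation"].
- Group B, switching: "If the participants will convert to the optional cohort, 1 day before the optional investigation phase". That later phase starts at the "Date of the first BDQ+CAM+EB intake for nonconverters came from Group B", so the rifamycin washout still counts as investigation phase.

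SAP 5.6.3.3 also plans that the number and percentage of participants with "QTc interval increases from baseline to the maximum postbaseline value will be summarized"; the sentence names no phase. SAP 5.6.3.1 plans shifts from baseline to the worst laboratory grade.

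Some displays are structured by time. SAP 5.6.2 lists "AEs by onset time (at 3-months interval"), with no denominator rule. SAP 5.6.3.3 gives QTc categories and ECG changes at each scheduled visit, and treatment-emergent ECG values over time. SAP 5.6.3.1 gives laboratory shifts, toxicity grades and markedly abnormal values over time. SAP 5.6.1 describes treatment duration but does not use it as a denominator.

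**The concern.** The percentage of participants with at least one event, the worst grade and the maximum of repeated ECGs all tend to rise with time observed. When the arms are observed for different planned lengths, a side-by-side reading mixes drug effect with length of observation. The imbalance comes from the phase definitions themselves and would remain with no dropout.

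Safety compared with rifamycin is a stated secondary objective, and protocol 2.3.1 names QT prolongation as a known risk of bedaquiline and clarithromycin. Protocol 9.2 and SAP 3 assume 10% conversion in Group B, so up to about 90% of that arm could be non-converters at Week 24 and candidates for the optional cohort. Depending on how many switch, a reader of the cumulative tables could take a difference in observation time for a harm or a benefit of bedaquiline.

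**Working it through.** The documents give no numerical figure for the safety comparison, so there is none to reproduce. The sizes below rest on stated assumptions.

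**Windows.** Protocol 6.8.2 lets the switch decision fall between the Week 24 assessment and Week 32 and requires a 2-week washout. Switchers therefore contribute 24 + 2 = 26 to 32 + 2 = 34 weeks. The Schedule of Activities footnotes on the optional cohort allow the decision to run past Week 32, so 34 is not a hard limit. Group A contributes 48 weeks and Group B non-switchers 60.

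**Adverse events, equal constant hazard.** Let I be the Group A incidence by Week 48, λ = −ln(1 − I)/48, and F(t) = 1 − exp(−λt). With a share s of Group B switching at week T, Group B shows s·F(T) + (1 − s)·F(60). The share is assumed: 50% to 100% of the 90% non-converters, so s = 0.45 to 0.90, with s = 0 as the other extreme.

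For I = 50%, λ = 0.01444; F(26) = 31.3%, F(34) = 38.8%, F(60) = 58.0%.

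| Share switching | T | Group B, I = 50% | Group B, I = 20% |
|---|---|---|---|
| 0.90 | 26 | 34.0% | 12.7% |
| 0.90 | 34 | 40.7% | 15.6% |
| 0.45 | 26 | 46.0% | 18.5% |
| 0.45 | 34 | 49.3% | 20.0% |
| 0 | – | 58.0% | 24.3% |

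**Balance point.** Mean planned windows agree when s·T + (1 − s)·60 = 48, that is s = 12/(60 − T): 35% at T = 26, 40% at T = 30, 46% at T = 34. Below that share Group B is observed longer; above it, Group A is.

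**Declining hazard.** Suppose the hazard after Week 12 is one quarter of the earlier hazard h, identical in both arms. For I = 50%, h·(12 + 36/4) = ln 2, so h = 0.0330; F(26) = 40.0% and F(60) = 54.7%. At s = 0.90 and T = 26, Group B shows 0.9 × 40.0 + 0.1 × 54.7 = 41.5%, against 34.0% under a constant hazard. For I = 20% the same case gives 15.9%, against 12.7%.

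**Maximum QTcF.** The Schedule of Activities has 15 postbaseline ECG visits to Week 48, 9 to Week 24, 11 to Week 32 and 18 to Week 60. Assume no drug effect and independent errors with SD 10 ms at baseline and at every visit. The chance that the maximum rise exceeds 30 ms is then 13.4% with 15 visits, 9.8% with 9, 11.1% with 11 and 14.9% with 18. The table is by intervention group, so switchers and non-switchers must be combined: 0.90 × 9.8 + 0.10 × 14.9 = 10.3%, up to 0.45 × 11.1 + 0.55 × 14.9 = 13.2%. Whole Group B is therefore 10.3% to 13.2% against 13.4% in Group A, a gap of 0.2 to 3.1 points.

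**Effect of the candidate fixes.** A Week 24 cut gives the same planned time in both arms whatever the hazard shape; under the constant hazard above both would show F(24) = 29.3%. Person-time rates also agree under a constant hazard: 0.01444 × 52.18 × 100, or about 75 per 100 person-years, in every group. They do not agree under the declining hazard: at s = 0.90 and T = 26, identical hazards give about 105 per 100 person-years in Group B against about 85 in Group A.

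**The case against.** The strongest reply is that much of the safety reporting already handles time. A reader might infer that the QTc and laboratory tables are not split by time at all. The SAP does not support that: 5.6.3.1 and 5.6.3.3 plan by-visit and over-time displays, and through Week 24 these compare the arms on equal planned time. The first two 3-month AE intervals also end at about the earliest switch. This part of the reply stands. What remains exposed is the cumulative AE tables, the worst-grade laboratory shift and, if it is cut by phase, the maximum-QTc table.

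A reader might also infer that the tables will overstate bedaquiline harm. That does not follow, because the direction depends on a switching share nobody knows in advance. Protocol 6.8.2 bars some non-converters from switching, including those on an individualized regimen, and protocol 4.2 lets investigators continue rifamycin. At 45% switching at Week 34 the distortion almost vanishes; with no switching it reverses.

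Comparing Group A with switchers alone (13.4% against 9.8% to 11.1%) would overstate the ECG effect, because the table is by whole group. The 10 ms SD and the independence of visits have no source in the documents. If the maximum-QTc table included follow-up, Group A would have 18 visits, the same as non-switchers and still more than switchers.

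Finally, SAP 5.6 makes safety descriptive, so no test depends on these percentages. That limits the consequence to interpretation. It does not remove it, since adjacent percentages are how the arms will be compared.

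**Conclusion.** The point holds for the cumulative tables: AEs, SAEs, AEs of special interest, severity, relatedness, discontinuation, worst laboratory grade and, if cut by phase, maximum QTc change. As written, they can show a between-arm difference when hazards are equal. Against 50% in Group A, Group B could read anywhere from 34% to 58% depending on switching, under an equal constant hazard. A hazard that falls over time narrows this (41.5% in place of 34.0% in the most extreme switching case). The maximum-QTc effect is at most about 3 points over the 45% to 90% switching range, under the assumed error model. Events confined to the first 24 weeks are little affected. The documents establish neither the direction nor the actual size. This is a worthwhile and inexpensive addition to the reporting plan; it does not affect the primary analysis.

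**What to change.** In SAP 5.6.2, 5.6.3.1 and 5.6.3.3:

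- Keep the full-phase tables and add a Day 1 to Week 24 between-arm table for AEs, SAEs, AEs of special interest, worst laboratory grade and maximum QTcF change.
- State the window for the maximum-QTc and worst-grade tables, including whether Group A follow-up counts.
- Accompany the full-phase AE tables with person-time incidence or Kaplan-Meier cumulative incidence of first event, censored at the end of the phase. Note beside them that person-year rates assume a roughly constant hazard, and that censoring at a switch is not random, because protocol 6.8.2 selects non-converters without an AE that forces clarithromycin or ethambutol to stop.

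The cost is SAP wording and repeated table shells; no new data are needed. The downside is more tables. The Week 24 table does not cover later bedaquiline exposure, so it supplements the full-phase tables and cannot replace them.

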### **5.6.3. Additional Safety Assessments**

#### **5.6.3.1. Clinical Laboratory Tests**

Clinical laboratory tests will be displayed for the participants included in the safety analysis set.

Descriptive statistics (n, mean, SD, minimum, median and maximum) and graphical displays will be presented for chemistry, hematology, and urinalysis laboratory tests at scheduled time points by intervention arm and study phase.

Change/percent change from baseline to each scheduled time point will be summarized for chemistry, hematology, and urinalysis tests and displayed by intervention group.

An abnormality (toxicity grade and/or abnormality based on normal ranges) will be attributed to the baseline and postbaseline values.

Postbaseline abnormalities will be compared with their corresponding baseline result:

- For toxicity grades, treatment emergent (TE) will be concluded if the postbaseline value is worse than the baseline value.
- For abnormalities based on normal range and/or criteria: If the postbaseline value is above the upper limit and the baseline value is below the upper limit (eg, Normal or Low), then the postbaseline abnormality will be considered TE. The same applies to the postbaseline value being below the lower limit with the baseline value being above the lower limit (eg, Normal or High).
- If the baseline value is missing, a postbaseline abnormality will always be considered as TE.

Number and percentage of participants with clinically important laboratory values and/or markedly abnormal values (defined as grade 3 or higher) will be presented by intervention group over time. Listing of clinically important laboratory values will be defined according to DMID definitions.

Plots of mean (+/-SE) values and changes from baseline over time for clinically important laboratory parameters will be presented by intervention arm and analysis phase.

Shift tables will be provided summarizing the shift in laboratory values from baseline over time with respect to abnormality criteria (low, normal, high).

Descriptive statistics by toxicity grade over time will be presented. Shift summaries from baseline toxicity grade to the worst toxicity grade will also be presented.

Shift summaries from baseline laboratory value to the worst grade in chemistry and hematology tests will be presented.

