Lung function test		X r								X							X			X	(X)
Chest CT s	X									X							X			X	(X)
Pharmacokinetics (PK)																					
Blood sampling for PK of BDQ (Group A)		X u	X u	X t	X t	X u		X u	X t		X u		X t				X u				
Blood sampling for PK of CAM		X u	X u			X u		X u			X u										
Safety assessment																					
Adverse events		Continuously																			
12-lead ECG v	X	X	X	X	X	X	X	X	X	X	X	X	X	X	X	X	X	X	X	X	X
Physical examinations, vital signs w	X	X	X	X	X	X	X	X	X	X	X	X	X	X	X	X	X	X	X	X	X
Clinical laboratory tests x	X	X		X		X		X			X			X			X			X	X

	Screening a	Investigation b																Follow-up (Group A)/ Investigation (Group B)			Early discontinuation/ Switch to ITR f
Day (D)/Week (W)	-W10 to D0	Baseline D1 c	W2	W4	W6	W8	W10	W12	W16 d	W20 d	W24 d	W28 d	W32 d	W36 d	W40 d	W44 d	W48 d,e	W52 d	W56 d	W60 d	
Study day	-70 to 0	1	15±2	29±2	43±2	57±2	71±2	85±2	113±3	141±3	169±3	197±4	225±4	253±4	281±4	309±4	337±4	365±4	393±4	421±4	before W60
Audiology, visual examinations y		X		X cc		X cc		X			X			X			X			X	(X)
Fundoscopy dd		X									X						X			X	(X)

Note: (X)=If available

Key: CAM=clarithromycin; CT=computed tomography; D=day; ECG=electrocardiogram; FSH=follicle-stimulating hormone; HIV= human immunodeficiency virus, ITR=Individualized treatment regimen; MGIT=mycobacterium growth indicator tube; MIC= minimal inhibitory concentration; NTM=nontuberculous mycobacterial; PK=pharmacokinetics; QOL-B=Quality of Life-Bronchiectasis; SGRQ= St. George's Respiratory Questionnaire; SoA=schedule of activities; VNTR: variable number tandem repeat, W=week; WGS: whole genome sequencing; WOCBP: woman of childbearing potential.

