### ***Pancreatic Amylase Elevation***

Grade 1 ( $> 1.0$  to  $\leq 1.5 \times \text{ULN}$ ) or Grade 2 ( $> 1.5$  to  $\leq 2.0 \times \text{ULN}$ ):

Participants may continue to take the study intervention and should be carefully evaluated and followed closely.

Grade 3 ( $> 2.0$  to  $\leq 5.0 \times \text{ULN}$ ) or Grade 4 ( $> 5.0 \times \text{ULN}$ ):

For asymptomatic Grade 3 pancreatic amylase elevations with no history or concomitant disease of pancreatitis, participants may continue to take the study intervention but should be carefully evaluated and followed closely. For confirmed Grade 4 elevations of pancreatic amylase, participants will have to permanently discontinue the study intervention. If there is clinical

evidence of pancreatitis and amylase of Grade 3 or higher, participants will have to permanently discontinue the study intervention.

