### ***Musculoskeletal System and Cardiac Muscle***

#### **Myalgia**

Grade 1 (with no limitation of activity):

Participants may continue to take the study intervention and should be carefully evaluated and followed closely.

Grade 2 (muscle tenderness at site other than injection site or with moderate impairment of activity) or Grade 3 (severe muscle tenderness with marked impairment of activity) or Grade 4 (frank myonecrosis):

Participants will have to permanently discontinue the study intervention but can continue in the study. Creatinine phosphokinase should be fractionated for creatine kinase myocardial band (CPK-MB) subunit. Participants having confirmed  $\geq$ Grade 2 myalgia with Grade 3 ( $3.0$  to  $6.0 \times$  ULN) elevation in CPK-MB, or Grade 4 ( $>6.0 \times$  ULN) elevation in CPK-MB subunit will have to permanently discontinue the study intervention.

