### **Clinical Laboratory Tests**

Laboratory data will be summarized by type of laboratory test. Reference ranges and markedly abnormal results (specified in the SAP) will be used in the summary of laboratory data. Descriptive statistics will be calculated for each laboratory analyte at baseline and for observed values and changes from baseline at each scheduled time point. Changes from baseline results will be presented in pre- versus postintervention cross-tabulations (with classes for below, within, and above normal ranges). Frequency tabulations of the laboratory abnormalities will be made. A listing of participants with any laboratory results outside the reference ranges will be provided. A listing of participants with any markedly abnormal laboratory results based on DMID scale (defined in SAP) will also be provided.

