### Protocol-Required Safety Laboratory Assessments

Laboratory Assessments	Parameters		
Hematology (Local Laboratory)	Platelet count Red blood cell count (RBC) Hemoglobin Hematocrit	RBC Indexes: MCV MCH % Reticulocytes	White Blood Cell (WBC) count with Differential: Neutrophils Lymphocytes Monocytes Eosinophils Basophils
Clinical Chemistry (Central Laboratory)	Sodium Potassium Chloride Bicarbonate Blood urea nitrogen (BUN) Serum creatinine (screening and Day 1) Glucose Aspartate aminotransferase (AST)/Serum glutamic-oxaloacetic Alanine aminotransferase (ALT)/Serum glutamic-oxaloacetic Gamma-glutamyltransferase (GGT)	Total bilirubin (direct, indirect) Alkaline phosphatase (ALP) Creatine phosphokinase (CPK) CPK myocardial band (CPK-MB) Lactic acid dehydrogenase (LDH) Uric acid Calcium Calcium corrected for albumin* Phosphate Albumin Total protein Cholesterol Triglycerides Magnesium Pancreatic amylase C-reactive protein (CRP)	
All events of ALT <math>\geq 3 \times</math> upper limit of normal (ULN) and bilirubin <math>\geq 2 \times</math> ULN (<math>>35\%</math> direct bilirubin) or ALT <math>\geq 3 \times</math> ULN and international normalized ratio (INR) <math>>1.5</math>, if INR measured which may indicate severe liver injury (possible Hy's Law), must be reported as a serious adverse event (excluding studies of hepatic impairment or cirrhosis).
 
*: When albumin is lower than 4.0 g/dL, calcium corrected for albumin is calculated by the following formula:
 
 
Calcium corrected for albumin (mg/dL) = calcium (mg/dL) + <math>0.8 \times (4.0 - \text{albumin [g/dL]})</math>
 

Laboratory Assessments	Parameters
Routine Urinalysis (Local Laboratory)	Dipstick (for qualitative urine, common kit provided by sponsor must be used); Specific gravity pH Glucose Protein Blood Ketones Bilirubin Urobilinogen

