## **10.4.3. Severity Criteria**

An assessment of severity grade will be made using Section 10.7, [Appendix 7: A Division of Microbiology and Infectious Diseases \(DMID\) Adult Toxicity Table \(November 2007\)](#). In case of the event is not listed in DMID table, the severity grade will be made accordingly.

**Grade 1 (Mild):** Transient or mild discomfort (<48 hours); no medical intervention/therapy required.

**Grade 2 (Moderate):** Mild to moderate limitation in activity - some assistance may be needed; no or minimal medical intervention/therapy required.

**Grade 3 (Severe):** Marked limitation in activity, some assistance usually required; medical intervention/therapy required, hospitalizations possible.

**Grade 4 (Life-threatening):** Extreme limitation in activity, significant assistance required; significant medical intervention/therapy required, hospitalization or hospice care probable.

The investigator should use clinical judgment in assessing the severity of events not directly experienced by the participant (eg, laboratory abnormalities).

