**6.10. Appendix 10 Laboratory Toxicity Grading**

The grading scale use for lab assessments is based on DMID and defined as follows.

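### SAP Appendix 10 has no CPK-MB row and leaves an amylase of 5.1 x ULN without a grade, so the outputs graded from it do not match the bands in protocol Section 8.2.6 (minor)

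*SAP*

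**What the plan says.** Protocol Section 9.4.6 leaves the definition to the SAP: "Reference ranges and markedly abnormal results (specified in the SAP) will be used in the summary of laboratory data".

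SAP Section 5.6.3.1 takes this up. Counts and percentages of participants with "clinically important laboratory values and/or markedly abnormal values (defined as grade 3 or higher) will be presented by intervention group over time". The same section also plans summaries by toxicity grade over time and shifts from baseline to the worst grade.

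The grades come from SAP Appendix 10, which opens: "The grading scale use for lab assessments is based on DMID and defined as follows". A hematology, a chemistry and a urinalysis table follow.

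Protocol Section 8.2.6 gives its own bands for two analytes and attaches drug-stopping rules to them.
- **CPK-MB:** Grade 3 is 3.0 to 6.0 x ULN and Grade 4 is above 6.0 x ULN. The rule names confirmed myalgia of Grade 2 or higher with Grade 3 CPK-MB, or Grade 4, and ends: "elevation in CPK-MB subunit will have to permanently discontinue the study intervention".
- **Pancreatic amylase:** Grade 3 is above 2.0 and up to 5.0 x ULN, and Grade 4 is above 5.0 x ULN. "For confirmed Grade 4 elevations of pancreatic amylase, participants will have to permanently discontinue the study intervention".

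Protocol Appendix 2 lists both analytes among the required central-laboratory chemistry tests.

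**The concern.** The protocol grades two required tests and uses the grades in stopping rules, while the scale that the SAP prints for its graded tables omits one test and sets a different Grade 4 bound for the other. A statistical programmer who follows Appendix 10 literally cannot give any CPK-MB value a grade, and cannot grade an amylase of 5.1 x ULN, which the protocol calls Grade 4 and treats as a permanent stop if confirmed.

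At stake is agreement between the graded laboratory tables and the rules under which participants were managed. Protocol Section 8.3.7 names skeletal muscle, heart and pancreas among the target organs for careful monitoring, so a reader of the safety report may look for these analytes in the graded tables.

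**Working it through.** The plan gives no figure to reproduce here. The check sets the two documents side by side.

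**1. Is there a CPK-MB row?** Rows in SAP Appendix 10: 5 hematology + 20 chemistry + 1 urinalysis = 26. Rows for CPK-MB: 0. The chemistry row of the protocol's Schedule of Activities has 7 scheduled post-baseline visits (Weeks 4, 8, 12, 24, 36, 48 and 60). Appendix 10 assigns no CPK-MB grade at any of them.

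**2. Amylase bands (x ULN).**

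| Grade | Protocol 8.2.6 | SAP Appendix 10 |
|---|---|---|
| 1 | >1.0 to 1.5 | 1.1 - 1.5 |
| 2 | >1.5 to 2.0 | 1.6 - 2.0 |
| 3 | >2.0 to 5.0 | 2.1 - 5.0 |
| 4 | >5.0 | >5.1 |

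On a one-decimal grid from 1.0 to 7.0 x ULN, exactly one value that is Grade 3 or 4 in the protocol gets a missing or different grade in the SAP. That value is 5.1, which is protocol Grade 4 and has no SAP grade.

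**3. Is this the table's rounding style?** Of the 26 rows, 25 have a Grade 4 (proteinuria does not). In 24 of the 25, Grade 4 starts exactly where Grade 3 ends. Examples are AST 3.0-8.0 then >8, BUN 5.1-10 then >10, creatinine 3.1-6 then >6, and hemoglobin 6.5-7.9 then <6.5. Amylase (2.1-5.0 then >5.1) is the only break, so it looks like a slip.

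**4. What does the gap do to the counts?** Placing 5.1 in either neighbouring grade makes it Grade 3 or higher, so any sensible repair keeps it in that count. The choice of neighbour changes only the Grade 4 count. If the value is left ungraded, as the text literally has it, it drops out of both.

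**5. What does a CPK-MB grade decide?** Under Section 8.2.6, myalgia of Grade 2 or higher already stops study drug, so Grade 3 CPK-MB adds no further stop. Grade 4 CPK-MB is a separate stop only if that clause is read apart from the myalgia condition. The documents do not settle which reading is meant.

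**The case against.** The strongest reply is that little is lost.

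- **Other summaries cover these analytes.** SAP Section 5.6.3.1 allows an abnormality to rest on a toxicity grade or on the normal range. CPK-MB and amylase therefore keep descriptive statistics by visit and low/normal/high shifts. Protocol Section 9.4.6 adds a listing of out-of-range results. Clinically relevant laboratory changes are recorded as adverse events, and for their severity "An assessment of severity grade will be made using Section 10.7". SAP Section 5.6.2 tabulates adverse events by severity and by discontinuation, and SAP Appendix 8 summarises myopathy and acute pancreatitis SMQs by group. This stands, and it is why the point is minor. These routes do not repair the Appendix 10 graded outputs.
- **Not every analyte needs a grade.** Total CPK, LDH, albumin and several other required tests also have no row. That is true, but CPK-MB differs because the protocol prints Grade 3 and 4 bands for it.
- **The DMID table may differ from Section 8.2.6.** Protocol Appendix 7 is blacked out, so this cannot be checked. A reader might infer that no CPK-MB elevation can appear anywhere in the quoted table. The documents do not support that, because the clinically important part of the table may follow DMID definitions outside Appendix 10. The point is limited to grades taken from Appendix 10.
- **The amylase gap can be made to look larger.** On a two-decimal grid, 19 values that are protocol Grade 3 or 4 have no SAP grade: 9 from 2.01 to 2.09 and 10 from 5.01 to 5.10. The first 9 only reflect the one-decimal style seen in other rows (BUN 2.5 then 2.6, creatinine 1.5 then 1.6) and are not a separate error.

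**Conclusion.** Both discrepancies stand on the text. Appendix 10 omits a required test that the protocol grades, and its amylase Grade 4 bound disagrees with Section 8.2.6. The size is 0 of 26 rows for CPK-MB and one ungraded amylase value at one-decimal precision. How many participants would be affected is unknown.

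Severity is minor. SAP Section 5.6 makes all safety summaries descriptive, and the primary analysis is untouched. A reader might infer that participants could be wrongly kept on or taken off drug. The documents do not support this, because stopping decisions follow protocol Section 8.2.6 and not SAP Appendix 10.

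The conclusion assumes that Appendix 10 is applied as printed and that amylase is expressed to one decimal of ULN before grading; the SAP states no rounding rule.

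**What to change.** Make two edits to SAP Appendix 10.
1. Add a CPK-MB row using the Section 8.2.6 bands: Grade 3 = 3.0-6.0 x ULN, Grade 4 = >6.0 x ULN. Fill Grades 1 and 2 only if the DMID table gives them.
2. Change amylase Grade 4 from >5.1 to >5.0 x ULN. This matches Section 8.2.6 and closes the break. Check the bound against the unredacted DMID table at the same time.

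The cost is one added row and one corrected bound. Graded laboratory tables already programmed would be re-run, and no new data are needed.
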